8.3.3 Missing Transfusion Data

Subjects who withdraw from study prior to day 29 will have missing data for the secondary endpoint, "RBC transfusion or hemoglobin \leq 8.0 g/dL from week 5 (day 29) to EOETP"; these subjects will be excluded from the analysis of this endpoint.

8.3.4 Missing Hemoglobin Data

For the endpoint "Change in hemoglobin from baseline to EOETP", the last available post-baseline hemoglobin, not occurring in the 28 days after a RBC transfusion, will be used to calculate change in the event that the EOETP value is missing or occurred within 28 days after a RBC transfusion. Subjects without a post-baseline value that did not occur in the 28 days after a RBC transfusion and subjects with a missing baseline hemoglobin will be excluded from the analysis of this endpoint.

8.3.5 Missing Adverse Event and Concomitant Medication Data

Missing data for adverse events and concomitant medication will not be imputed. Adverse event and concomitant medication data will be analyzed as observed with the exception of missing dates. Missing or incomplete dates for adverse event or concomitant medication data will be handled according to the following rules in order to estimate when the event occurred/medication was taken and the duration:

8.3.5.1 Imputing Partial or Missing Start Dates

- If the year is unknown, then the date will not be imputed and will be assigned a missing value.
- If the month is unknown, then:
 - If the year matches the first dose date, then impute the month and day of the first dose date.
 - Otherwise, assign January.
- If the day is unknown, then:
 - If the month and year match the first dose date, then impute the day of the first dose date.
 - Otherwise, assign '01'.

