7.1.9 Concomitant Medication and Red Blood Cell Transfusion

Concomitant medications, procedures of interests (eg, radiotherapy, anti-cancer surgery), and RBC transfusion details will be collected from screening to EOTP. The reason for the RBC transfusion and any adverse events (including VTE) associated with RBC transfusion will be recorded on the CRFs. Concomitant medications include, but are not limited to, the use of any prohibited ESA or non-protocol specified dose of IP, hematopoietic growth factor, iron supplement, anti-hypertensive agent, anti-cancer therapy including chemotherapeutic agents, and anticoagulation therapy. Collection of information on ESA usage and anti-cancer therapy will be continued at pre-specified intervals during the LTFU period.

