Unspecified/mixed thromboembolic events include thromboembolic events where the vessel type is either unspecified or a mix of arterial and venous. These events will be coded using MedDRA version **20.0** (or higher) and identified using the sub-SMQ 20000083 ("embolic and thrombotic events, vessel type unspecified and mixed arterial and venous") or more appropriate query available at the time of analysis.

Time to Progression (TTP)

Time from randomization to date of radiographic disease progression. Subjects without progression will be censored on the date of their last disease assessment. Disease progression will be based on the investigator's assessment of scans using the version of RECIST specified in the protocol at the time of subject enrollment.

Treatment Group

Subjects were randomized to 1 of 2 treatment groups: darbepoetin alfa (500 μ g) Q3W or placebo Q3W in a 2:1 allocation.

Treatment-emergent Adverse Event

A treatment-emergent adverse event is an adverse reported via the adverse event summary eCRF with an onset date between study day 1 and 30 days after the last dose of IP, inclusive, with one exception: VTEs and adverse events associated with RBC transfusions can have an onset date of 30 days after the last dose of IP or the EOTP visit, whichever is later.

6. Analysis Sets

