6.3 Per Protocol Sets

Since poor adherence to the protocol could have the potential to bias the results towards a conclusion of non-inferiority, a sensitivity analysis will be performed on a per protocol set to confirm results from the primary analysis set. The sensitivity analysis using this per protocol set will be performed for overall survival and **progression free survival**. The per protocol set will include subjects in the primary analysis set who meet all of the following additional criteria **(also see Appendix A):**

- had metastatic (Stage IV) or advanced stage IIIB with malignant pleural effusion (prior to Amendment 3) NSCLC
- no disease progression prior to study day 1
- no history of or current cancer diagnosis other than NSCLC
- had baseline pre-chemo scan prior to randomization (for PFS only)
- had an ECOG performance status of 0 or 1 at screening
- had a life expectancy > 6 months based on the judgment of the investigator at screening
- did not receive erythropoiesis stimulating agents within the 28 days prior to screening
- did not have a documented history of pure red cell aplasia
- dosed per protocol through week 7 with the correctly assigned investigational product (this includes receiving planned doses and dose adjustments per section 6.1.2 of the protocol)
- received first-line cyclic chemotherapy for NSCLC during the treatment period
- did not receive erythropoiesis stimulating agents, other than investigational product as defined in the protocol, during the treatment period.

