8.3.5.2 Imputing Partial or Missing Stop Dates

- If the year is unknown or "ongoing" is indicated, then the date will not be imputed and will be assigned a missing value.
- If the month is unknown, then assign December.
- If the day is unknown, then assign the last day of the month.

In no case will the stop date be later than the EOS date

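### SAP 8.3.5.1 can impute the first dose date as a start date without checking a known stop date or the period in which the record was collected

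*SAP*

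**What the plan says.** SAP 8.3.5 applies one set of rules to two kinds of record: "Missing or incomplete dates for adverse event or concomitant medication data will be handled according to the following rules". For start dates, 8.3.5.1 distinguishes three cases.

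- Year unknown: the date stays missing.
- Month unknown: "If the year matches the first dose date, then impute the month and day of the first dose date"; otherwise January is used.
- Day unknown: "If the month and year match the first dose date, then impute the day of the first dose date"; otherwise the first of the month is used.

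The only bound in 8.3.5 is on the other end of the record, in 8.3.5.2: "In no case will the stop date be later than the EOS date". Nothing limits the imputed start.

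SAP Section 5 defines a treatment-emergent adverse event as one "with an onset date between study day 1 and 30 days after the last dose of IP, inclusive", with a longer window for VTEs and transfusion-related events. Study day 1 therefore counts.

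Protocol 7.1.9 lists ESAs and anti-cancer therapy among concomitant medications and adds: "Collection of information on ESA usage and anti-cancer therapy will be continued at pre-specified intervals during the LTFU period". Protocol 6.3 proscribes no therapy during long-term follow-up (LTFU).

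**The concern.** A first-dose default is sensible when nothing else is known about an event. Here it also applies when other data in the same record, or the visit at which it was collected, show that the date is wrong.

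Pre-dose events are in the database by design. Protocol 7.1.10 collects serious adverse events from consent and other adverse events from randomization. Screening may last 21 days (protocol 5.1), and randomization may come up to 4 days before the first dose (protocol 5.3). Moving such an event to day 1 against its own stop date inflates the treatment-emergent tables and leaves a start after a stop.

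For follow-up therapy the date itself is the analysis variable. The cross-in model in SAP 9.6.1 switches a placebo subject to exposed when ESA use begins, and the safety endpoint table in SAP 9.6 plans the same adjustment for PFS. SAP 9.6.12 summarizes NSCLC treatment in the treatment period and up to first progression. A therapy begun in follow-up but dated to day 1 lands in the wrong period in each.

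**Working it through.** The plan states no count of partial dates, so there is no figure to reproduce. The check applies the rule literally to worked dates.

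Assumed for illustration: first dose 20 March 2014.

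| Record | Known part | Start under SAP 8.3.5.1 |
|---|---|---|
| SAE, truly 5 to 12 March 2014 | March 2014; stop 12 March 2014 | 20 March 2014 |
| SAE, truly from 27 February 2014 | February 2014 | 1 February 2014 |
| ESA in LTFU, truly 10 November 2014 | 2014 | 20 March 2014 |
| ESA in LTFU, truly 10 November 2014 | November 2014 | 1 November 2014 |
| ESA in LTFU, truly 10 April 2015 | 2015 | 1 January 2015 |

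**Pre-dose event (row 1).** The imputed start is 8 days after the event's own stop (20 − 12). Under SAP Section 5 the event is treatment-emergent. If the start may not exceed the stop, the latest date consistent with March 2014 is 12 March, and the event stays pre-dose. Row 2 shows the limit of the problem: where the known month differs from the first-dose month, the rule leaves the event pre-dose.

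**Follow-up therapy (row 3).** From 20 March to 10 November 2014 is 11 + 30 + 31 + 30 + 31 + 31 + 30 + 31 + 10 = 235 days. A placebo subject would be coded as exposed for 235 days of ESA-free time. The subject must have survived that time to start the ESA, so death-free time is credited to exposure, which pulls the estimated ESA hazard ratio for survival downward. Now assume EOTP on 15 August 2014 and no earlier LTFU contact. The earliest date in 2014 not before EOTP is 15 August. The start is then 16 + 30 + 31 + 10 = 87 days early instead of 235, and falls outside the period between first dose and EOTP.

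**How often a month-missing LTFU record is misplaced.** Let E be days from first dose to EOTP and G be days from EOTP to the true start, with first-dose dates spread evenly over the year. The imputed date escapes the treatment period only if 1 January falls between EOTP and the true start.

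- Share dated into the treatment period = 1 − G/365. G = 30: 92%. G = 90: 75%. G = 180: 51%.
- Share dated exactly to study day 1 = 1 − (E + G)/365, or 0 if negative. E = 90, G = 30: 67%. E = 365: 0%.

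With only the day missing, the share dated on or before EOTP is 51% for G = 15, about 2% for G = 30 and 0% for G = 90 or more. E and G are assumptions; the documents give neither. All shares are conditional on the record having a partial date, and how many do is not stated.

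**The case against.** The strongest reply is that dating an unplaced event to day 1 is an accepted conservative choice in a safety table. That stands. With first-dose dates spread over the year, about 92% of day-missing events in a 4-day pre-dose window, and about 57% in a 25-day window (21 + 4), would move to day 1. A reader might take these shares as the size of the defect. They are not: they include records with nothing to contradict day 1. Only records with contrary information are in error.

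Other stronger readings also go too far.

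- **Per-protocol set.** SAP 6.3 requires that a subject "did not receive erythropoiesis stimulating agents, other than investigational product as defined in the protocol, during the treatment period", so a reader might infer that misdated ESA use removes subjects from this set. SAP Appendix A ties that exclusion to deviation code TA 507, and no document says the code is derived from imputed dates.
- **Unknown year.** A reader might infer that events with no year vanish from the treatment-emergent tables. The SAP leaves the date missing but does not state that consequence, and such records should be rare.
- **Before-first-dose box.** The documents show this only on the contingency SAE form (protocol Appendix C). The stop date, a required attribute under protocol 9.1.2, is the more general check.
- **Certainty of reclassification.** SAP 9.6.4 defines treatment-emergent as onset after the first dose is given. An imputed day 1 carries no clock time, so its status there is unclear; under SAP Section 5 it is not.

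It can also be said that protocol 13.3 provides for consistency checks and site queries, and that protocol 7.7 asks for administration dates at LTFU contacts. Both make the problem rarer. Neither says what to do with a date that stays partial. One could further argue that concomitant medication collection formally ends at EOTP, so LTFU records fall outside the rule. But protocol 7.1.9 lists ESA and anti-cancer therapy as concomitant medication in the same paragraph, and the SAP gives no other rule for them.

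**Conclusion.** The point holds in a limited form. Followed literally, SAP 8.3.5.1 gives a wrong date in two situations: a pre-dose event in the first-dose month with a known pre-dose stop, and a year-only ESA or anti-cancer record from follow-up in the first-dose year. In later years the January default can likewise fall before EOTP. The first situation affects the treatment-emergent tables; the second affects the exploratory cross-in model, which the SAP already says to interpret with caution, and the descriptive NSCLC treatment summaries.

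The primary OS analysis is untouched, and the per-protocol ESA exclusion may be. The number of affected records cannot be derived from the documents and is probably small. This is a minor correction, worth making because the rule as written can produce impossible records and the data needed to prevent them are already collected.

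**What to change.** Add two sentences to SAP 8.3.5.1.

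1. An imputed start date may not be later than a known stop date; if it would be, use the latest date consistent with the known date parts and the stop date.
2. For ESA or anti-cancer therapy first recorded in LTFU, where the known date parts and any stop date allow it, impute the earliest date consistent with them that is not before EOTP, or not before the previous LTFU contact if that is later; otherwise keep the known date parts.

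The condition in the second sentence matters. With EOTP on 15 August 2014, a therapy reported late as July 2014 must stay in July and not be pushed past its own recorded month. Keep the day-1 default for adverse events where nothing contradicts it.

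The cost is a small change to the date-imputation program. One trade-off remains: a therapy that truly began before EOTP, but was first reported in follow-up with only the year, would be dated after EOTP. Routine collection through EOTP makes that the less likely error. SAP 7.2 describes database cleaning and lock as still to come, so the rule can be settled before the analysis is run.

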8.3.5.2 Imputing Partial or Missing Stop Dates

- If the year is unknown or "ongoing" is indicated, then the date will not be imputed and will be assigned a missing value.
- If the month is unknown, then assign December.
- If the day is unknown, then assign the last day of the month.

In no case will the stop date be later than the EOS date

8.4 Detection of Bias

To check for the introduction of bias, the following analyses will be performed:

- Comparing the percentage of subjects between treatment groups who withdraw from the treatment prematurely (e.g., withdrawing before completion of chemotherapy or radiographic disease progression)
- Calculating the rate of cross-in (subjects randomized to placebo who receive erythropoiesis stimulating agents at any point after randomization) in the placebo arm (if applicable)
- Comparing the percentage of subjects between treatment groups who receive an RBC transfusion when the hemoglobin value at the time of transfusion was ≤8.0 g/dL (number of subjects transfused is the denominator)
- Cross-tabulating the values of the stratification factors recorded in the IVRS versus the case report forms to assess the degree of misspecifications of the stratification factors at randomization.

Analyses that examine the impact of these potential sources of bias will be described in the sections that describe the analyses for the primary and secondary endpoints; **however, these tables may not be included in the clinical study report.**

8.5 Outliers

Potential data outliers will be identified **during** the **analysis dataset programming process** and queried as appropriate. Any data points that are identified as possible outliers, but are subsequently verified through the query process, will be treated as valid data and analyzed accordingly.

8.6 Distributional Characteristics

The statistical assumptions for each method of inferential testing or estimation will be assessed. If the assumptions for the distributional characteristics of endpoints are not met, these will be described and further analyses may be carried out using transformations of endpoint values or alternative inferential or estimation methods. The use of transformations or alternative analysis methods will be fully justified in the final study report.

8.7 Validation of Statistical Analyses

Programs will be developed and maintained, and output will be verified in accordance with current risk-based quality control procedures.

Tables, figures, and listings will be produced with validated standard macro programs where standard macros can produce the specified outputs.

The production environment **for statistical analyses** consists of Amgen-supported versions of **statistical analysis** software; **for example, the** SAS **System version 9.4** or later **or using R.**

9. Statistical Methods of Analysis

9.1 General Considerations

- Continuous variables will be summarized by the mean, standard deviation, median, and range. The confidence interval and standard error for the mean will also be summarized for efficacy variables that are continuous.
- Categorical variables will be summarized by the number and percentage in each category.
- Time to event variables will be summarized with hazard ratios, Kaplan-Meier curves, Kaplan-Meier quartiles, the number of subjects per treatment group, the number of subjects censored, and the number & percent of subjects with events.
- For stratified analyses, the value for the stratification factors will be taken from IVRS rather than the case report forms; a cross-tabulation of the values recorded in the IVRS versus the case report forms will be generated to assess degree of misspecifications of the stratification factors at randomization.
- To preserve the overall significance level for the study, statistical testing of the primary and secondary endpoints will follow a hierarchical structure. First, the primary endpoint of OS will be tested. If darbepoetin alfa is demonstrated to be non- inferior to placebo with respect to OS, PFS will be formally tested. If darbepoetin alfa is demonstrated to be non-inferior to placebo with respect to PFS then the incidence of RBC transfusions or a hemoglobin ≤ 8.0 g/dL will be formally tested. If non- inferiority is demonstrated for both OS and PFS and superiority is demonstrated for the transfusion endpoint, superiority will then be tested for both OS and PFS using the Hochberg procedure to adjust for multiplicity. For endpoints that are not designated as primary or secondary, statistical testing will be considered descriptive and no adjustments will be made for multiplicity.
- Where confidence intervals are provided, these will be 2-sided at the 95% level, unless otherwise specified

9.2 Subject Accountability

The number and percentage of subjects screened, randomized, and who received at least one dose of investigational product will be presented (a footnote will include the date of first subject randomized and the end of study date). The number and percentage of subjects who withdrew prematurely will be tabulated by the reason for withdrawal. **Since the study was terminated early,**

the number of subjects who were still on-study as of the termination date (dosing terminated 8 May 2017; data collection terminated 7 June 2017) will be tabulated by treatment group.

The number and percentage of subjects in the primary analysis set, the radiographic endpoint primary analysis set, the transfusion from week 5 to EOETP primary analysis set, full analysis set, **and the safety analysis set** will be presented. The number and percentage excluded from the analysis sets will be tabulated by the reason for exclusion.

A cumulative distribution plot will depict subject randomization over time; this will include a footnote of the number of subjects randomized but not dosed. In addition, the number and percentage of subjects randomized will be tabulated by study site and by the stratification factors (ie, geographic region, tumor histology and screening hemoglobin value).

A cumulative distribution plot will depict subject discontinuation from the treatment period over time. Each reason for ending the treatment period will be depicted by a line with separate plots for each treatment group

9.3 Important Protocol Deviations

Important Protocol Deviations (IPDs) categories are defined by the study team before the first subject's initial visit and updated during the IPD reviews throughout the study prior to database lock. These definitions of IPD categories, subcategory codes, and descriptions will be used during the course of the study. Eligibility deviations are defined in the protocol. The final IPD list is used to produce the Summary of IPDs table and the List of Subjects with IPDs.

9.4 Demographic and Baseline Characteristics

The following demographic and baseline characteristics will be summarized by treatment group and for both treatment groups combined:

- Age, age group (18-64, 65-74, 75-84, ≥85 as well as ≥65 and ≥75), sex, and race
- Weight, height and body mass index (BMI)
- Stratification factors (geographic region, tumor histology, screening hemoglobin). A cross tabulation of stratification factors according to the IVRS compared to the case report form values will be generated. If there are major differences between the IVRS and case report form stratification factors, then a sensitivity analysis of the primary and secondary endpoints (overall survival, progression-free survival and incidence of transfusion or hemoglobin ≤8 g/dL) may be done.
- ECOG performance status, tumor histology, and presence of measurable disease

- Smoking status and significant medical history including hypertension, prior VTEs, prior ATEs, and diabetes
- Type of therapy for NSCLC used prior to randomization (chemotherapy, targeted therapy and/or radiotherapy) and on study day 1 (eg, chemotherapy with or without any anti-EGFr or anti-angiogenic agents)
- Baseline hematology values for hemoglobin level (at start of chemotherapy, at screening/randomization and at baseline), platelet count, absolute neutrophil count, white blood cell count, and baseline laboratory values for serum iron, serum ferritin, transferrin saturation (TSAT), total iron binding capacity, creatinine, total bilirubin, alanine aminotransferase (ALT), aspartate aminotransferase (AST) and serum erythropoietin (EPO) level.

These characteristics will be summarized for the primary analysis set.

9.5 Efficacy Analyses

The following table summarizes the planned efficacy analyses:

Endpoint	Primary Summary and Analysis Method (Specify Analysis Set)	Sensitivity Analysis		
Primary Efficacy Endpoint – n/a (primary endpoint is a safety endpoint)				
Secondary Efficacy Endpoints				

Table 9-1. Efficacy Endpoint Summary Table

Endpoint	Primary Summary and Analysis Method (Specify Analysis Set)	Sensitivity Analysis
Transfusion or Hemoglobin ≤ 8.0 g/dL from Week 5 (day 29) to EOTP– Transfusion from Week 5 to EOETP	Summarize the number and percent of subjects who are transfused or have hemoglobin ≤ 8.0 g/dL, the difference in percent transfused between treatment groups; the common odds ratio; and the Cochran- Mantel-Haenszel statistic and p- value in the primary analysis set; calculate odds ratio of the treatment effect Dataset: Transfusion from Week 5 to EOETP Primary Analysis Set	 Transfusion from Week 5 (day 29) to EOETP Dataset: Transfusion from Week 5 to EOETP Transfusion or Hemoglobin ≤ 8.0 g/dL from Week 5 (day 29) to EOETP by stratification factors Dataset: Transfusion from Week 5 to EOETP Transfusion or Hemoglobin ≤ 8.0 g/dL from Week 5 (day 29) to EOETP adjusted for stratification factors [logistic regression model(s)] Dataset: Transfusion from Week 5 to EOETP Repeat analysis for subjects impacted vs not impacted by early study termination Dataset: Transfusion from Week 5 to EOETP Repeat analysis for subjects of FOETP Repeat analysis for targeted study day 1 for subjects who delayed start of investigational product Dataset: Week 5 to EOETP using the Full Analysis Set (starting from targeted day 1)
Transfusion from Week 5 (day 29) to EOETP when Hemoglobin is ≤ 8.0 g/dL at the Time of Transfusion	Summarize the number and percent of subjects with a transfusion when the hemoglobin is ≤ 8.0 g/dL at the time of transfusion by treatment group; the common odds ratio; and the Cochran-Mantel-Haenszel statistic and p-value in the primary analysis set; calculate odds ratio of the treatment effect Dataset: Transfusion from Week 5 to EOETP Primary Analysis Set	N/A

Endpoint	Primary Summary and Analysis Method (Specify Analysis Set)	Sensitivity Analysis
Transfusion or Hemoglobin ≤ 8.0 g/dL from Week 1 (day 1) to EOETP	Summarize the number and percent of subjects with a transfusion or hgb≤ 8.0 g/dL by treatment group by treatment group; the difference in percent transfused between treatment groups; the common odds ratio; and the Cochran-Mantel- Haenszel statistic and p-value Dataset: Primary Analysis Set	 Transfusion from Week 1 (day 1) to EOETP Dataset: Primary Analysis Set Transfusion from Week 1 (day 1) to EOETP when hemoglobin is ≤ 8.0 g/dL at the Time of Transfusion Dataset: Primary Analysis Set
Change in Hemoglobin from Baseline	Summarize the change in hemoglobin from baseline to Week 13, Week 16 and EOETP by treatment group and provide t-test p-value. Dataset: Primary Analysis set; use central laboratory hemoglobin values	 Box plot of median, mean 25th and 75th percentiles, minimum and maximum over time by randomized treatment group Dataset: Primary Analysis set; use central laboratory hemoglobin values Plot change in hemoglobin values from baseline over time by randomized treatment group Dataset: Primary Analysis set; use central laboratory hemoglobin values Plot change in hemoglobin values from baseline over time by randomized treatment group Dataset: Primary Analysis set; use central laboratory hemoglobin values Repeat analysis for targeted study day 1 for subjects who delayed start of investigational product Dataset: Full analysis set using targeted day 1 as the baseline use central laboratory hemoglobin values

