4.1.3 Laboratory

- Hemoglobin level ≤ 11.0 g/dL as assessed by the local laboratory; sample obtained within 7 days prior to randomization (retest in screening is acceptable)
- Adequate serum folate (≥ 2 ng/mL) and vitamin B₁₂ (≥ 200 pg/mL) levels assessed by central laboratory (supplementation and retest acceptable) during screening

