4.1 Planned Covariates

- Stratification factors:
 - Geographic region (some regions may be combined for analysis):
 - Region 1: Belgium, Germany, Israel, Italy, Luxembourg, Netherlands, Spain, Switzerland, South Africa, UK
 - Region 2: Bulgaria, Czech Republic, Greece, Poland, Romania, Russia, Serbia, Slovenia, Ukraine
 - Region 3: Argentina, Brazil, Chile, Hong Kong, South Korea, Malaysia, Mexico, Philippines, Taiwan
 - Region 4: India
 - Region 5: Canada, United States (reference group)
 - Region 6: China
 - Region 7: Japan (analyzed as part of Region 3)
 - Histology: Squamous vs non-squamous cell (reference group)
 - Screening hemoglobin level: <10 g/dL vs >=10 g/dL (reference group)
- Potentially clinically important covariates:
 - NSCLC platinum-based chemotherapy vs. other chemotherapy (reference group)
 - NSCLC Targeted therapy (anti-EGFr or anti-angiogenic agents or other) vs. none (reference group)
 - o Baseline serum erythropoietin: ≤100 mU/mL vs >100 mU/mL (reference group)
 - History of VTEs: yes vs. no (reference group)

Note that the reference group will be coded a "0" in any statistical modeling including stratification factors and/or covariates.

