4.2 Subgroups

The subgroup of subjects who were not impacted by the early study closure to may be analyzed as a sensitivity analysis for the primary and secondary endpoints (overall survival, progression-free survival and incidence of transfusion or hemoglobin ≤ 8 g/dL) as well as the analyses of investigational product dosing and changes in dosing. For the analysis of overall survival, this would include subjects who were lost to follow-up or who died prior to 8 June 2017. For progression-free survival, this would include subjects who were withdrawn, lost to follow-up or who died or had radiographic progression prior to 8 June 2017. For incidence of transfusion or hemoglobin ≤ 8 g/dL, investigational product dosing and changes in dosing, this would include subjects who were withdrawn, lost to follow-up or completed chemotherapy prior to 8 June 2017.

These subgroups and planned covariates will be re-examined and appropriately recategorized before the analysis. If a subgroup only contains less than 10% of the total study population, it will be combined with another subgroup in the analysis.

5. Definitions

Best Overall Response

A subject's best overall response during the study will be categorized in the following order: complete response, partial response, stable disease, disease progression, not evaluable, missing due to clinical progression, and missing for reasons other than clinical progression.

Change in hemoglobin from baseline to EOETP

The change score is the difference between the baseline hemoglobin value and the EOETP value (i.e., EOETP value – baseline value). Post-baseline hemoglobin values within 28 days after a RBC transfusion will not be used in the calculation of change. The last available post-baseline hemoglobin, not occurring in the 28 days after a RBC transfusion, will be used to calculate change in the event that the EOETP value is missing or occurred in the 28 days after a RBC transfusion. Subjects without a post-baseline value that did not occur in the 28 days after a RBC transfusion and subjects missing a baseline hemoglobin will be excluded from the analysis. Only central laboratory values will be used. Because the EOETP will vary by subject, the change in hemoglobin from baseline will also be summarized at specific time points of week 13 and week 16.

Event of Interest	Search Strategy	Scope
Ischaemic Heart Disease, including	Ischaemic Heart Disease SMQ	Narrow
MI		
Mortality and/or Tumor	Malignancies SMQ	Narrow
Progression		

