9.5.3 Analyses of Exploratory Efficacy Endpoint(s)

An analysis similar to the analysis for transfusion or hemoglobin \leq 8.0 g/dL from week 5 to EOETP will be done for transfusion or hemoglobin \leq 8.0 g/dL from day 1 to EOETP (with a sensitivity analysis of incidence of a transfusion from day 1 to EOETP). These will be based on the Primary Analysis Set.

Descriptive statistics for change in hemoglobin from baseline will be provided at weeks 13 and 16 and graphs will be provided for hemoglobin over time (box plot) and change in hemoglobin from baseline over time (line plot) by treatment group. These will all be based on the Primary Analysis Set.

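### Change in hemoglobin is compared by an unadjusted t-test although baseline hemoglobin and the strata are on file; ANCOVA would generally be more precise, by an amount the documents do not fix

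*SAP*

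**What the plan says.** SAP Table 9-1 covers change in hemoglobin at Week 13, Week 16 and EOETP, and its instruction for the comparison is "by treatment group and provide t-test p-value". The sensitivity entries in that row are plots and a repeat from the targeted day 1; none names an adjustment. SAP 9.5.3 adds only summaries and graphs: "Descriptive statistics for change in hemoglobin from baseline will be provided at weeks 13 and 16".

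The outcome is defined in SAP Section 5: "The change score is the difference between the baseline hemoglobin value and the EOETP value". Only central-laboratory values count. SAP 8.3.4 states that "subjects with a missing baseline hemoglobin will be excluded from the analysis of this endpoint", so every analysed subject has a baseline value. The strata are also on file. Under SAP 9.1, for stratified analyses, "the value for the stratification factors will be taken from IVRS rather than the case report forms". One of those strata is screening hemoglobin, split at 10 g/dL (SAP 4.1).

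The other main comparisons use the strata:
- transfusion or low hemoglobin, by Cochran-Mantel-Haenszel (SAP 9.5.2);
- objective response, by the same method (SAP 9.6.3);
- OS and PFS, by stratified Cox models (SAP 9.6.1 and 9.6.2).

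SAP 2.1 lists change in hemoglobin among the other endpoints. SAP 9.1 sets the status of such tests: "For endpoints that are not designated as primary or secondary, statistical testing will be considered descriptive".

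**The concern.** A change score fixes the slope of follow-up on baseline at 1. ANCOVA estimates that slope from the data. Unless the true slope is 1, the change score leaves outcome variance unexplained that baseline could explain, and the interval for the treatment difference is wider than it need be. It also leaves any chance difference in baseline in the estimate, where ANCOVA would adjust for it.

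Hemoglobin change is the exception in a plan that otherwise uses the randomization factors, although one of those factors is itself a hemoglobin measurement. In addition, Table 9-1 asks for a p-value but no estimated difference with an interval. With a trial of this size, a p-value alone says little about how large the hemoglobin effect is. What is at stake is the precision and usefulness of one descriptive result, not a conclusion of the trial.

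**Working it through.** **The plan's own figure.** The documents give no SD, correlation, target difference or power for change in hemoglobin. The only power figure is for OS: about 93% with 2700 deaths, margin 1.15, 1-sided 0.025 and 2:1 allocation. It reproduces: √(2700 × 2/3 × 1/3) × ln 1.15 − 1.96 = 24.49 × 0.1398 − 1.96 = 1.46, which is 92.8% power. It has no bearing on this endpoint.

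**Formula.** Let s be the follow-up SD, k the baseline SD divided by the follow-up SD, and ρ the baseline-to-follow-up correlation, all taken to be the same in both arms.
- Variance of the change score: s²(1 + k² − 2kρ).
- Residual variance after adjusting for baseline: s²(1 − ρ²).
- Difference: s²(k − ρ)².
- Share of variance removed by ANCOVA: (k − ρ)² / (1 + k² − 2kρ).

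This share is never negative. It is zero when k = ρ, because the true slope ρ/k is then 1.

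**Case 1: equal SDs (assumed, k = 1).** The share reduces to (1 − ρ)/2:

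| ρ | 0.2 | 0.3 | 0.4 | 0.5 | 0.6 | 0.7 | 0.8 |
|---|---|---|---|---|---|---|---|
| Variance removed | 40% | 35% | 30% | 25% | 20% | 15% | 10% |

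**Case 2: narrower baseline (assumed, k = 0.5 to 0.8).** Protocol 4.1.3 requires "Hemoglobin level ≤ 11.0 g/dL as assessed by the local laboratory". That truncates the baseline distribution, while follow-up values have no such entry limit, so k below 1 is plausible:

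| k | ρ = 0.3 | ρ = 0.4 | ρ = 0.5 | ρ = 0.6 |
|---|---|---|---|---|
| 0.5 | 4.2% | 1.2% | 0.0% | 1.5% |
| 0.6 | 9.0% | 4.5% | 1.3% | 0.0% |
| 0.7 | 15.0% | 9.7% | 5.1% | 1.5% |
| 0.8 | 21.6% | 16.0% | 10.7% | 5.9% |

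Any further gain from the strata is unknown and is not counted here.

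**What this means in g/dL.** Take 2549 subjects at 2:1 (about 850 and 1699) and an assumed change SD of 1.5 g/dL.
- SE = 1.5 × √(1/850 + 1/1699) = 0.063, so the 95% half-width is 1.96 × 0.063 = 0.124 g/dL.
- A 10% variance cut gives 0.124 × √0.90 = 0.118.
- A 22% cut gives 0.124 × √0.78 = 0.110.
- A 40% cut gives 0.124 × √0.60 = 0.096.
- If only half the subjects are evaluable, the unadjusted half-width is 0.175.

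For an assumed true difference of 0.5 g/dL, the unadjusted t-test already has at least 98.8% power across change SDs of 1 to 2 g/dL and 50% to 100% of subjects evaluable.

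**The case against.** The strongest reply is that nothing depends on this. The endpoint is outside the testing hierarchy and SAP 9.5.3 treats it as exploratory. Precision is ample, and the efficacy endpoint with a formal test is already stratum-adjusted. All of this stands, and it limits the point to a minor one. Table 9-1 does place the row beneath its heading for secondary efficacy endpoints, but neither SAP 2.1 nor the protocol's endpoint list makes it secondary.

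Several stronger readings are tempting, and the documents do not support them.
- A reader might infer a definite loss of a quarter to a third of the precision. That needs equal SDs together with a correlation of about 0.33 to 0.5. Neither is in the documents, and the entry cap makes equal SDs doubtful.
- A reader might infer that the t-test is biased. Under randomization it is not, and chance imbalance is already part of its standard error. Stratifying on screening hemoglobin and enrolling 2549 subjects also make a material baseline imbalance unlikely.
- A reader might infer that the change score ignores the correlation. Its variance contains ρ; it uses the correlation, though not optimally.
- A reader might infer a conflict between protocol and SAP. The method text in protocol 10.6.2.4 is not visible, so no comparison is possible.

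One further point cuts both ways. Values within 28 days after a transfusion are discarded, and subjects left without a usable value are dropped. Transfusion may differ by arm, so the analysed set may be selected. ANCOVA would adjust for any resulting baseline difference, but it would not cure the selection.

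**Conclusion.** The point holds as a small efficiency improvement. The planned comparison is valid but leaves out a covariate that every analysed subject has, and it departs from the stratum-adjusted approach used for the other main endpoints. The size of the gain cannot be derived from the documents. Under assumptions, the variance reduction is about 10% to 40% with equal SDs and correlation 0.8 to 0.2, and about 0% to 22% with a baseline SD of 0.5 to 0.8 of the follow-up SD and correlation 0.3 to 0.6. Both ranges assume the same SDs and correlation in the two arms. The omission itself is certain; its size is not. No formal conclusion of the trial is affected.

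**What to change.** In SAP Table 9-1, replace the t-test with ANCOVA of change in hemoglobin on treatment, continuous baseline central-laboratory hemoglobin and the IVRS stratification factors. Report the adjusted treatment difference with a 95% CI at Week 13, Week 16 and EOETP. The t-test can stay as a supportive result. The text should say that baseline here is the SAP's central-laboratory value, because the protocol glossary equates baseline hemoglobin with the local screening value.

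The cost is one line of SAP text and one model statement, with no new data and no imputation. With Japan analysed within Region 3, the model adds at most 5 region terms, 1 for histology, 1 for screening hemoglobin and 1 for baseline, or 8 terms in all, which is negligible at this sample size. The change should be made before database lock, which SAP 7.2 describes as still to come.
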